3.3.4.1 CH-2000-02 (Migraine Phase 1)

Study CH-2000-02 was a randomized (1:1), double-blind, placebo-controlled study conducted at three centers and examined the safety and efficacy of nasal CO₂ in the treatment of acute migraine. The CO₂ or nitrogen (control) was administered from hospital medical gas cylinders using disposable nosepieces. Subjects (n=54) self-selected a gas flow rate ranging from 0.20 L/min (3.3 mL/sec) to 0.69 L/min (11.4 mL/sec), depending on their own preference. Subjects were continuously monitored for pCO₂ levels, heart rate, electrocardiogram (ECG), respiratory rate, respiratory pattern, and blood pressure.

There were no SAEs reported in this study. Adverse events were mostly limited to application site irritation and included atypical sensations in the nasal cavity (discomfort, burning, stinging), watery eyes, throat discomfort, bad or unusual taste or smell, and dizziness/lightheadedness/vertigo. Compared to pre-dose control, the study showed no clinically meaningful differences in the pCO₂ of subjects who received CO₂. There were no significant differences between CO₂ and placebo gases in any of the physiologic parameters measured at any time point.

The study provided preliminary evidence that nasal CO₂ is not systemically absorbed to any measurable degree and appears to be safe.

3.3.4.2 CH-2002-01 (Migraine Phase 2a)

Study CH-2002-01 was a randomized (1:1), double-blind, placebo-controlled, multi-center study and examined the safety and efficacy of nasal CO₂ in the treatment of acute migraine. The gas was delivered via hand-held dispenser (CAP-2, an earlier design of the current CO₂ drug delivery system) at a subject-selected flow rate of either approximately 0.3 L/min or approximately 0.9 L/min. Subjects were known International Headache Society (IHS)-defined migraineurs who were allowed to treat at any severity of pain at baseline (i.e., pain could be mild, moderate or severe), across multiple migraines.

There were no SAEs reported in this study. Adverse events most frequently reported included administration site reactions (irritation) and nausea.

The study demonstrated a 2-hour pain-free response of 36% in the CO₂ group (55 subjects) compared with 10% in placebo group (60 subjects), p<0.01, for the first attack. Relief was rapid with the majority of all responders in the CO₂ group reporting no pain at 30 minutes. Stratification according to pain at baseline showed a substantial improvement in the 2-hour pain-free response rate (52% CO₂, 10% placebo, p<0.01) for subjects with mild pain at baseline.

This study therefore provided preliminary evidence that nasal CO₂ is a potentially effective treatment for acute migraine.

3.3.4.3 CH-2004-03 (Migraine Phase 2b)

A randomized (2:1), double-blind, placebo-controlled, multi-center study examined the safety and efficacy of nasal CO₂ in the treatment of acute migraine. The gas was delivered via a hand-held dispenser (CAP-3, an earlier design of the current CO₂ drug delivery system) at flow rate of approximately 0.6 L/min. Subjects were known IHS-defined migraineurs treating a typical migraine at moderate or severe pain.

There were no SAEs reported. The most common AEs were administration site irritation (i.e., stinging, burning, numbness, tingling).

The study showed a 2-hour pain-free response of 23% for CO₂ (89 subjects) versus 4% for placebo (45 subjects), p<0.01. The trial included a pulsed dosing arm where the efficacy comparison to placebo was not statistically significant.

The trial provided further evidence that nasal CO₂ may be an effective treatment for acute migraine. Statistically significant efficacy was observed at 2 hours with rapid onset of effect and the effect was sustained at 24 hours.

3.3.4.4 C112 (Mild Headache Study)

Study C112 was a randomized, double-blind, placebo-controlled study to evaluate the safety and efficacy of nasal CO₂ in the treatment of mild headache in migraineurs. This was an adaptively designed study that used a two-step randomization process. First, eligible subjects were assigned to either active or placebo. Then, upon experiencing a qualifying headache, subjects would call into the Interactive Voice Response System (IVRS) to receive their dosing regimen assignment.

Two-hundred ninety-two subjects were randomized into Study C112 and 244 completed the study. Of the 244 subjects, 102 subjects (69 active and 33 placebo) dosed 10 sec/nostril 1 time, 49 subjects (29 active and 20 placebo) dosed 20 sec/nostril 1 time, 21 subjects (15 active and 6 placebo) dosed 40 sec/nostril 1 time, 42 subjects (31 active and 11 placebo) dosed 10 sec/nostril 4 times, and 30 subjects (21 active and 9 placebo) dosed 20 sec/nostril 4 times.

The safety profile of nasal CO₂ was similar to what has been seen in prior studies with the most common adverse events being nasal discomfort and lacrimation. There were no serious adverse events in subjects who treated a headache with the study drug and no discontinuations due to adverse events.

The study showed that lower doses appear to be efficacious, and higher doses do not seem to add to efficacy. The 10 sec/nostril 1 time dose group was the most efficacious in this study (showing a 38.5% pain-free at 2 hours versus 25.8% for placebo), with the 10 sec/nostril 4 times showed similar efficacy (showing a 36.7% pain-free at 2 hours versus 18.2% for placebo). None of the groups achieved statistical significance against corresponding placebo, but the 10 sec/nostril 1 time dose group showed strong statistical trends towards efficacy (Bayes p=0.09). The study was primarily designed to select the appropriate dose for future studies, and determined that dose to be 10 sec/nostril which can be repeated up to 4 times.

3.3.4.5 C113 (Phase 3, Moderate to Severe Migraine Study)

Study C113 was a multi-center, double-blind, placebo-controlled, parallel group trial that evaluated the safety and efficacy of nasal, non-inhaled administration of CO₂ in the treatment of moderate to severe migraine.

Subjects were allowed to treat up to a total of 4 moderate to severe migraines within a 56-day treatment period. Headaches treated with the study drug (nasal CO₂ or placebo) were to be at least 48 hours apart.

Each dose consisted of an administration of 10 sec/nostril. If subjects still had pain and/or any other symptoms after the initial dose then they were permitted to take a dose after completing the symptom assessment at 15, 30, and/or 60 minutes after the initial dose. Thus, subjects could

Protocol 15-001CA
Nasal CO₂

have taken up to 4 doses of study drug to treat a headache. Subjects with an ongoing headache at 2 hours were permitted to take rescue medication.

A total of 35 subjects were enrolled in this study. This study was performed in collaboration with the Navy's Advanced Medical Development Program and medicated through the Omnibus program. Due to a low enrollment rate and limited funding available to conduct this study, this study was closed prior to meeting the enrollment goal of 450 subjects.

The analysis of all subjects treated (CO₂ = 17; Placebo = 13) did not show statistical significance in any of the four co-primary endpoints (pain free, nausea/vomiting free, photophobia free, or phonophobia free) at two hours after the initiation of treatment.

The safety profile of nasal CO₂ was similar to what has been seen in prior studies. The most common adverse event reported was nasal discomfort (CO₂ = 36.8%, placebo = 12.5%). All reported events typically resolved with cessation of administration. There were one SAE; it was due to a bicycle accident and unrelated to the study drug.

The most reported AEs were mild or moderate in severity. Of the 15 severe AEs reported, only 4 (nausea [n=1], nasal discomfort [n=2], and migraine [n=1]) were deemed related to study drug or study device; however, all 4 of these AE resolved with the cessation of application of the study drug/device. There were 2 discontinuations due to AEs. One was due to severe nausea and identified as being probably related to study drug; however, this subject was assigned to placebo. The other was due to neck pain and deemed unrelated to study drug and/or study device; the subject withdrew from the study because non-allowed medication was required for the treatment of the neck pain.

3.3.5 Clinical Evaluations in Allergic Rhinitis

To date, approximately 975 subjects with allergic rhinitis have participated in clinical trials to evaluate the safety and preliminary efficacy of single doses of nasal CO₂ compared to a placebo control. In addition, a study was conducted to assess the consumer experience of CO₂ nasal spray in subjects with nasal congestion. One-hundred forty-seven subjects participated in that study. The doses administered in the allergic rhinitis studies have been smaller than those used for migraine, with the highest being approximately 1.2 L. The data from these studies are summarized briefly below.

3.3.5.1 SAR-2005 (Seasonal Allergic Rhinitis Single-Dose Study)

Study SAR-2005 was a double-blind, placebo-controlled, in-clinic, single-center study conducted to evaluate the safety and efficacy of a single dose of nasal CO₂ on the symptoms of seasonal allergic rhinitis (SAR).⁹ Eighty-nine subjects were treated with 60 seconds per nostril of either CO₂ (60 subjects) or placebo (29 subjects). The study tested one CO₂ dose of approximately 1.2 L (60 sec/nostril, approximately 0.6 L/nostril) versus placebo (air). There were no serious

adverse events (SAEs) reported. Nasal stinging or burning and watery eyes were the most common adverse events observed in this study.

In this study, a single dose (two 60-second nasal CO₂ administrations) resulted in rapid (10 minutes) and sustained (\geq 4 hours) relief of nasal symptoms (i.e., rhinorrhea, nasal congestion, nasal itching, and sneezing) compared to placebo.

3.3.5.2 C211 (Perennial Allergic Rhinitis Single-Dose Study)

Study C211 was a randomized (2:1), double-blind, placebo-controlled, in-clinic, multi-center study and examined the safety and efficacy of nasal CO₂ on the symptoms of perennial allergic rhinitis (PAR). The study tested two dose durations (10 and 30 sec/nostril) and two flow rates (0.3 and 0.6 L/min) for CO₂ versus placebo (no gas).¹ The primary endpoint was mean change from baseline in total nasal symptom score (TNSS, the sum of the scores of rhinorrhea, average score the right and left nostril congestion, nasal itching, and sneezing) at 30 minutes, separately comparing the 10 and 30 sec/nostril dosing groups. A total of 348 subjects (previously diagnosed with PAR) were randomized and treated.

There were no SAEs reported in this study. The treatment was generally well-tolerated and the most frequent AEs reported were nasal discomfort, lacrimation increased, headache, rhinalgia, rhinorrhea, and throat irritation.

The study provided further evidence that nasal CO₂ may be a safe and effective treatment for both the nasal and non-nasal symptoms (i.e., lacrimation, eye redness, ear/throat itching, eye itching) of PAR. It had a rapid onset of effect that was sustained for several hours compared to placebo.

3.3.5.3 C213 (Perennial Allergic Rhinitis Multi-Dose Study)

Study C213 was a randomized, double-blind, placebo-controlled, single-center, cross-over study to evaluate the effect of nasal, non-inhaled CO₂ on nasal congestion using acoustic rhinometry in subjects with PAR. Twenty (20) subjects were randomized to receive study drug in one of four treatment sequences. Each sequence consisted of the same four treatments in different order. These four treatments were:

- Dose A: Nasal CO₂ (0.5 SLPM) for 5 sec/nostril
- Dose B: Nasal CO₂ (0.5 SLPM) for 10 sec/nostril
- Dose C: Nasal CO₂ (0.5 SLPM) for 30 sec/nostril
- Dose D: Placebo (0.0 SLPM, no gas) for 30 sec/nostril

All 20 subjects completed all four treatments and completed the study.

Protocol 15-001CA
Nasal CO₂

CO₂ was delivered via a nosepiece that was attached to a CO₂ cylinder by plastic tubing. The flow rate was controlled by a flow control valve at 0.0 SLPM for the placebo dose for (Dose D) and 0.5 (\pm 0.05) SLPM for the active doses (Doses A, B, and C).

No consistent changes in nasal congestion were seen as measured by acoustic rhinometry.

3.3.5.4 C215 (Seasonal Allergic Rhinitis Multi-Dose Study)

Study C215 was a randomized, double-blind, placebo-controlled, multi-center study to evaluate the efficacy and safety of nasal CO₂ administered twice daily for 14 days in the treatment of seasonal allergic rhinitis. Four-hundred fifty-three (453) subjects met the randomization criterion of a minimum average score of 6 on the total nasal-symptom score (TNSS, a 0 - 3 scale to evaluate the severity of congestion, runny nose, itchy nose, and sneezing) and were randomized, 229 to the CO₂ treatment and 224 to the placebo treatment. Of the subjects randomized, 451 (99.6%) had at least one administration of the study drug and 447 (98.7%) completed the study.

CO₂ and placebo (no gas) were administered via hand-held dispensers. Subjects completed symptom diaries every morning and evening over the 14-day treatment period.

The baseline characteristics were similar between the two groups with respect to age, sex, ethnicity, and race. The reflective Total Nasal Symptom Score (TNSS) at baseline was 9.6 ± 1.7 in the CO₂ group and 9.3 ± 1.7 in the placebo group.

An analysis of treatment effects over the entire 14-day treatment period noted that the change from baseline in reflective total nasal symptom scores for treatment compared to control subjects were 2.0 and 1.7, respectively ($p=0.1440$).

While the primary analysis of efficacy for the 14-day treatment did not show a significant benefit, statistically significant changes from baseline in TNSS were seen after the first dose on Day 0. The changes from baseline in instantaneous TNSS for treatment compared to control subjects at 30 minutes were -2.4 and -1.6, respectively ($p=0.0001$), and at 6 hours were -2.2 and -1.5, respectively ($p=0.0139$).

3.3.5.5 C216 (Phase 2, Seasonal Allergic Rhinitis)

Study C216 was a randomized (2:1), double-blind, placebo-controlled, multi-center, parallel group, pilot study to evaluate the efficacy and safety of nasal, non-inhaled carbon dioxide used as-needed, up to 6 times per day, for 14 days in subjects with SAR. Thirty-two (32) subjects who completed at least 2 SAR episode diaries per day and had a TNSS of 8 out of a maximum of 12 for at least 2 of the SAR episodes during the 3 days prior to randomization were randomized, 19 to the CO₂ treatment and 13 to the placebo treatment. All 32 subjects completed the study.

Carbon dioxide and placebo (no gas) were administered via hand-held dispensers. Subjects completed instantaneous symptom diaries immediately prior to dosing (pre-dose assessment), 30 minutes after dosing (post-dose assessment) as well as reflective diaries in the mornings and evenings during the 14-day treatment period.

The baseline characteristics were similar between the two groups with respect to age, sex, ethnicity, and race. Subjects in both groups dosed an average of 3 times per day. Analysis of all treated episodes (CO₂=816, placebo=516) showed a statistically significant beneficial change in pre-dose TNSS and 30-minute post dose TNSS for CO₂ (-2.00) versus placebo (-1.49), effect size=-0.51, p<0.0001.

3.3.5.6 C218 (Phase 2, Seasonal Allergic Rhinitis)

Study C218 was a randomized (2:1), double-blind, placebo-controlled, multi-center, parallel group, pilot study to evaluate the efficacy and safety of nasal, non-inhaled carbon dioxide administered four times per day, for 14 days in subjects with SAR. Thirty-three (33) subjects met the randomization criterion of a minimum average reflective TNSS of 8 out of a maximum of 12 and were randomized, 22 to the CO₂ treatment group and 11 to the placebo group. All 33 subjects completed the study.

Carbon dioxide and placebo (no gas) were administered via handheld dispensers. Subjects completed instantaneous symptom diaries immediately prior to dosing (pre-dose assessment), 30 minutes after dosing (post-dose assessment) as well as reflective diaries in the mornings and evenings during the 14-day treatment period.

The baseline characteristics were similar between the two groups with respect to age, sex, ethnicity, and race. Analysis of all treated episodes (CO₂=1220, placebo=602) did not show a statistically significant beneficial change in pre-dose TNSS and 30-minute post-dose TNSS for CO₂ (-0.78) versus placebo (-0.65), effect size=-0.13, p<0.6302.

3.3.5.7 RH01910 (Phase 2, Nasal Congestion)

Study RH01910 was a multi-center, monadic, open-label two-part repeat-dose, consumer experience study in subjects with nasal congestion. In the first part of the study, recruited subjects were provided a description of a new treatment option. Interested subjects were offered the opportunity to enter the clinical study. Eligible subjects received one dose, 10 sec/nostril of nasal CO₂ in the study clinic under medical supervision. Afterward, subjects who wished to continue in the study were allowed to take the nasal CO₂ product home for an additional six days of use, 10 sec/nostril up to 4 times daily. Subjects used a diary to record the number of times the product was used and their nasal congestion symptoms before and after use.

This study showed that nasal CO₂ was perceived well in subjects with nasal congestion.

The nasal CO₂ was tolerated well in this study. Adverse events were mild and consistent with previous studies. No serious or unexpected adverse events were reported.

3.3.6 Clinical Evaluation in Temporomandibular Disorders

Study C301 was a randomized, placebo-controlled study to evaluate the safety and efficacy of nasal, non-inhaled administration of CO₂ in subjects with pain and other symptoms related to temporomandibular disorders (TMD). One-hundred (100) subjects were randomized and treated with CO₂ or placebo in a 2:1 randomization respectively. For both treatment groups, a single dose consisted of 2 sequential administrations which were to last for 30 seconds in each nostril (60 sec/dose). Subjects in the CO₂ group received up to 3.6 L of CO₂; subjects in the placebo group received up to 3.6 L of Air. The data from this study are summarized in the current Investigator's Brochure for Carbon Dioxide Drug Delivery System.

3.4 Risk/Benefits

The adverse events anticipated with nasal CO₂ include: administration site reactions (such as nasal passage irritation, tingling, burning, pain, rhinorrhea, congestion, etc.), increased lacrimation, nausea, headache, throat irritation, dysgeusia, dizziness, pharyngolaryngeal pain, epistaxis, parosmia, post-nasal drip, rhinalgia, rhinorrhea, migraine headache, upper respiratory tract infection and feeling cold. There is minimal risk of systemic effects of CO₂ as relatively small volumes are administered locally to the nasal cavity. Even if the product were inadvertently inhaled, the amount of CO₂ is minimal compared to the minute volume of respiration.

3.5 Dose Rationale

The trial is designed to evaluate a dose of nasal CO₂ at 10 sec/nostril administered up to 6 times for one attack in a cluster period.

The dose selected for evaluation in this study are based on safety data from the Phase 2 single-dose studies in SAR and PAR, the multi-dose study in SAR, as well as from three studies in patients with migraine, and a study in healthy volunteers as described in Sections 3.3.3, Section 3.3.4, and Section 3.3.5, respectively. Prior migraine studies evaluated a wide range of doses (from 10 sec/nostril 1 time [0.17 L] to 20 sec/nostril 4 times [1.67 L]). Single doses evaluated in allergic rhinitis (AR) studies have ranged from 0.1 L to 1.2 L of CO₂. In a SAR study, subjects were allowed to administer up to 1.0 L of CO₂ per day for two-weeks. Thus, the dose selected for evaluation in this study is within the range of doses used in previous studies. In these previous studies, nasal CO₂ was found to be safe.

3.6 Trial Conduct

This trial will be conducted in compliance with the protocol approved by the Institutional Review Board (IRB), Good Clinical Practice (GCP), and applicable regulatory requirements and standards. No amendment to the protocol or deviation from the protocol will be implemented without the prior review and approval of the IRB except where it may be necessary to eliminate an immediate hazard to a research subject. In such a case, the deviation will be reported to the IRB as soon as possible.

3.7 Population

The trial population will include men and women ages 18 years old and above who have an established diagnosis of cluster headache, as defined by International Classification of Headache Disorders (ICHD), third edition, beta version guidelines (ICHD-3 beta, Cephalgia 2013).³

4.0 TRIAL OBJECTIVES

4.1 Primary Objective

The primary objective of this trial is to evaluate the safety and efficacy of nasal CO₂ for the treatment of cluster headache.

4.2 Secondary Objectives

Key secondary objectives are to determine the effect of nasal CO₂ in the treatment of cluster headache:

- freedom from pain at 5-60 minutes
- headache relief at 5-60 minutes
- rescue medication usage
- subject satisfaction

5.0 TRIAL DESIGN

This is an open-label, investigator-sponsored, pilot study. Subjects agreeing to participate in the study and meeting the eligibility criteria assessed at the screening visit will be enrolled in the study. The length of time between screening and treatment will last between 0 days to a maximum of 12 weeks. Subjects who enter the screening phase during a cluster headache episode and meet the study eligibility criteria can immediately enter the treatment phase and may opt to treat their cluster headache episode in the clinic. Subjects who are not in a cluster

Protocol 15-001CA
Nasal CO₂

headache episode, who meet initial screening eligibility criteria, can remain in the screening phase for up to 12 weeks until their next cluster episode begins. Upon initiation of a cluster headache episode, subjects will enter the treatment period.

Subjects will be trained and demonstrate the proper use of the hand-held dispenser containing CO₂ calibrated to deliver 0.5 standard liters per minute (SLPM). This dispenser will be provided to subjects for use in the clinic or home. Subjects will be instructed to use the nasal CO₂ dispenser, 10 sec/nostril, as needed up to 6 times to treat one attack. Each dose must be separated by 3-5 minutes. Subjects should treat only one attack in a 24-hour period. Subjects may treat up to three cluster headache attacks during the treatment phase of this study. One hour after the first dose subjects can choose to treat with investigator-approved rescue medication. Subjects will be asked to complete an online diary after the completion of the dosing. Diary assessments will collect pain severity (0=none, 1=mild, 2=moderate, 3=severe), symptoms (such as tearing, nasal congestion, and running nose), nasal CO₂ usage, acute medication usage, satisfaction of treatment, number of cluster attacks, and unusual symptoms. Subjects will be contacted by phone within 3 days of the first use of the nasal CO₂ dispenser to assess adverse events (AEs) and medication usage. A total of 25 subjects will enter the treatment period and be instructed to treat up to three cluster headaches with nasal CO₂. Within 7 days of treating their last cluster headache episode, subjects will return for an end of study visit.

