5.6 Data Identification

Clinical data will be directly entered into the combined eSource/CRF forms by members of the study site personnel. Site personnel will be responsible for instructing subjects on the requirement for timely and daily completion of the electronic diary (eDiary). Subject-reported adverse events and concomitant medications collected during the out-subject treatment period will be recorded by the subject in the eDiary. This diary will be reviewed by the Investigator and/or the appropriate study site personnel, applicable information will be collected, recorded into the subject's eSource/eCRF. The electronic diaries will be automatically collected after the completion of each diary and stored with the subject's eSource/CRF documents. Subjects will record their headache-related symptom assessments as well as the details regarding the nasal CO₂ administration in an electronic diary.

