8.1.9 Subject Diary and Assessments

The primary and most of the secondary endpoint data will be collected from the electronic daily headache diary. Site personnel will be responsible for instructing subjects on the requirement for timely completion of the electronic diary. An email will be sent to subjects for completion of their headache diary containing a link to the diary. This link will take them to a survey queue

Protocol 15-001CA
Nasal CO₂

where all diaries will be available for completion. The diary for each headache should be completed during or immediately after each headache treated with nasal CO₂ and will document:

- Pain severity: (0=none, 1=mild, 2=moderate, 3=severe)
- Baseline pain severity
- Study medication usage
- Rescue medication usage
- Pain severity after initial treatment with nasal CO₂, symptoms at 5, 15, 30, and 60 minutes following treatment
- Headache resolution
- Unusual symptoms

All assessments must be completed as close as possible to the protocol-specified time of the assessment.

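### The plan sets no time for entering the baseline pain score, so the reference value of the primary endpoint may be recalled after open-label dosing

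*Combined protocol and SAP*

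**What the plan says.** Sections 5.1.1 and 10.3.1 define the primary endpoint relative to pain before treatment. Section 8.1.9 takes the data from the electronic headache diary, on a four-category scale from 0 (none) to 3 (severe).

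Three places speak to when the diary is filled in:

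- The synopsis and section 5.0: "Subjects will be asked to complete an online diary after the completion of the dosing".
- Section 8.1.9: "The diary for each headache should be completed during or immediately after each headache treated with nasal" CO₂. The same section adds: "All assessments must be completed as close as possible to the protocol-specified time of the assessment".
- Section 5.6 has sites instruct subjects on "timely and daily completion of the electronic diary (eDiary").

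Section 8.1.9 lists "Baseline pain severity" as one item of this diary and attaches no time to it. The only clock times given are 5, 15, 30 and 60 minutes after treatment. The dosing instructions (7.1.1 and 8.1.10), the training list (8.1.8), the schedule of events (8.2) and the carry-forward rule (10.2) contain no step for scoring pain before the first dose.

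**The concern.** For a given attack, one baseline score enters every change from baseline. In an open-label study the post-dose scores are exposed to knowledge of treatment however promptly they are entered. A baseline entered after dosing exposes the reference value as well: the subject rates the earlier pain already knowing how the attack responded. There is no control arm in which the same recall error would appear and offset it. A score that was not taken before the dose cannot be recovered at analysis, so this has to be settled in the data-collection instructions.

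**Working it through.** The plan gives no figure on this point to reproduce. The check has three parts.

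**1. What the timing sentences require of the baseline item.** Under 5.0, the diary follows dosing, so a baseline held in that diary is entered after dosing. Under 8.1.9, entry may be during the headache, which includes the minutes before the first dose, or immediately after it, which does not. The rule about keeping close to the specified time has no stated clock time to act on for baseline. Entry before the dose and entry after the attack both comply with 8.1.9. The sentences partly fit together, since the 60-minute score, product use and satisfaction can only be completed after dosing. What is missing is a separate rule for baseline.

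**2. How late the entry is under the 5.0 wording.** Inputs: 10 seconds per nostril and at most 1 minute between nostrils (7.1.1); doses 3-5 minutes apart and up to 6 per attack (5.2.1, 7.1.1). One dose lasts from 10 + 10 = 20 s (0.33 min) to 10 + 60 + 10 = 80 s (1.33 min). The plan does not say whether the gap runs from start to start or from end to start, so both are shown for d doses:

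- start to start: end of dosing = (d − 1) × gap + one dose length
- end to start: end of dosing = (d − 1) × gap + d × dose length

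| Doses | Start to start (min) | End to start (min) |
|---|---|---|
| 1 | 0.33-1.33 | 0.33-1.33 |
| 2 | 3.33-6.33 | 3.67-7.67 |
| 3 | 6.33-11.33 | 7.00-14.00 |
| 4 | 9.33-16.33 | 10.33-20.33 |
| 5 | 12.33-21.33 | 13.67-26.67 |
| 6 | 15.33-26.33 | 17.00-33.00 |

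For six doses on the fastest course: 5 × 3 + 0.33 = 15.33 min, or 5 × 3 + 6 × 0.33 = 17.00 min. A baseline entered after dosing is then at least 15-17 minutes late, and the 5- and 15-minute points have passed. With a single dose the minimum delay is about 0.3-1.3 minutes.

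**3. What a baseline error does to the result.** Read the endpoint as the largest reduction, with B the true baseline, e the recall error, and S the lowest score observed at 5, 15 or 30 minutes.

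- Minimum taken over observed scores: result = (B + e) − S, so e = ±1 moves it by exactly ±1.
- No score within 30 minutes, baseline carried forward under 10.2: result = (B + e) − (B + e) = 0, whatever e is.
- Some scores observed and baseline carried into an earlier gap: result = max(0, B + e − S), so a one-category error moves it by between 0 and 1 point.
- B = 3: e cannot be positive, because 3 is the top of the scale. Any error lowers the baseline and understates benefit.

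Which missing-data case applies is not settled. Section 10.2 makes carry-forward optional for the primary endpoint, while 10.10 says that the primary analysis makes no adjustment for missing values.

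**The case against.** The strongest reply is that the plan plainly intends an early score. The endpoint says pre-treatment, 8.1.9 lists baseline separately from pain after the initial treatment, and the closeness rule can be read as making pre-treatment the specified time. Section 7.2.3 places rescue after the one-hour assessment, which implies scoring while the attack is under way. Section 5.0 also allows treatment in the clinic, where staff could obtain the score. The diary screens and Directions for Use are not in the documents and may prompt for baseline. Section 8.1.9 describes a survey queue "where all diaries will be available for completion", so a separate baseline form may already exist.

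Much of this stands. It rules out the stronger reading that the plan directs subjects to score baseline from memory. It does not close the gap, because these passages fix the moment to which the score refers and leave open when it is entered.

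A reader might also infer that the delay is unlimited. That holds only for the 5.0 sentence taken alone; 8.1.9 sets a loose limit, immediately after the headache.

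The background gives modest support for the fix. In study C216, "Subjects completed instantaneous symptom diaries immediately prior to dosing (pre-dose assessment), 30 minutes after dosing (post-dose assessment"), and C218 is described in the same terms. Both are rhinitis studies with nasal symptom scores, and the migraine summaries describe no such step. They show that pre-dose entry has been used with this product, not that it is standard for headache.

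**Conclusion.** The point holds as a gap in the written plan: baseline may be recalled after open-label dosing, but need not be. Under the 5.0 wording the minimum delay is 15-17 minutes for a six-dose attack and about 0.3-1.3 minutes for one dose. A one-category error moves an attack's result by 1 point where the result rests on scores observed within 30 minutes, and by 0 where only baseline is carried forward. This assumes that the endpoint means the largest reduction and that the unseen diary screens do not already force pre-dose entry.

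A reader might infer that the trial would overstate benefit, or that its false-positive rate is inflated. The documents do not support either. They give no share of subjects recalling wrongly, no direction of error and no standard deviation of change, and upward error is impossible from a true baseline of 3. The amendment is worth making because it is cheap and the measurement cannot be repaired later, not because a bias has been shown.

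**What to change.** In the synopsis and section 5.0, say that the diary is finished after dosing, while the baseline and the 5-, 15-, 30- and 60-minute pain scores are entered at their own times. In 8.1.9, change the item to *baseline pain severity, entered before the first dose*, as a short time-stamped entry. Present it as a data-collection request and not as a condition for treating the attack.

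The entry should stand alone. Section 5.6 states: "The electronic diaries will be automatically collected after the completion of each diary". The completion time of one form that also holds the 60-minute score would not show when baseline was scored.

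Keep every attack in the primary analysis and report how many baselines were entered after the first dose, using the dose times recorded under 8.1.10. A sensitivity analysis without those attacks is optional; in a pilot of up to 25 subjects it may be small and may select on attack severity.

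The cost is two qualified sentences, one diary item and a brief entry at attack onset. Some attacks will still lack an on-time baseline, and the late-entry count is only as reliable as the subject-entered dose times. If the existing screens already collect baseline before dosing, only the wording needs to change.
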